#### 5.2.4 Electrocardiogram

The 12-lead ECGs will be performed as scheduled in the [Flow Chart](#). Twelve-lead ECGs (I, II, III, aVR, aVL, aVF, V1 – V6) will be recorded using equipment provided by a central ECG vendor. The ECGs will be recorded for at least 10-second duration after the subjects have rested for at least 5 minutes in a supine position and prior to lab sampling. Electrode placement will be performed according to the method of Einthoven/Goldberger (ankles and wrists). At time points indicated in the Flow Chart, single ECGs will be recorded. ECG recordings at planned time points may be repeated for quality reasons like alternating current artefacts, muscle movements and electrode dislocation. In this case the repeated ECG recordings will be used if quality was better.

The investigator or a designee will evaluate whether the ECG is normal or abnormal and whether it is clinically significant, if abnormal. The electronic version of the ECG is regarded as source data. Dated and signed printouts will be stored in the patient's medical file if there is no validated and certified e-medical record for ECG data.

Additional ECGs may be collected by the investigator for safety reasons. Clinically relevant findings noticed at Visit 1 should be reported as baseline conditions. Clinically relevant, abnormal findings noticed after Visit 1 should be reported as AEs and followed up and/or treated locally until the condition returns to normal or becomes stable condition.

All ECGs will be transmitted electronically to the central ECG vendor in order to enable a centralized and independent re-evaluation of all 12-lead ECGs. A centralized and independent re-evaluation will be done.

Central evaluation on an individual ECG level will be performed by the vendor and a report will be provided to the site. Decisions on eligibility for the trial and treatment or further follow-up of any findings are in the responsibility of the investigator.

## **5.2.5 Other safety parameters**

### **5.2.5.1 Assessment of suicidality**

Suicidal risk will be assessed by the C-SSRS. The C-SSRS is a semi-structured, investigator-rated interview, developed by clinical experts in cooperation with the FDA, assessing both suicidal behavior and suicidal ideation. It does not give a global score, but provides some categorical and some severity information specifically for behavior and ideation. The C-SSRS is completed by the interviewer and is captured using the rater station/tablet provided by the vendor.

The C-SSRS has been widely used in large multi-national clinical trials. The C-SSRS will be administered first at screening (Visit 1) (using the 'Baseline / Screening' version) with the aim to exclude subjects with active moderate or severe symptomatology within a specified time prior to screening.

After screening (Visit 1) the assessment 'since last visit' will be performed at each clinic visit ('Since Last Visit version'). The investigator is to review/consider the C-SSRS results for plausibility and clinical relevance. If the positive report is confirmed, appropriate actions for the subject's safety have to be initiated.

All C-SSRS reports of suicidal ideation type 4 or 5 and all reports of suicidal behavior must be reported as separate SAEs by the investigator.

For 'Self-injurious behavior, no suicidal intent' standard AE / SAE reporting rules are to be applied.

For each C-SSRS report of suicidal ideation type 1, 2 or 3 after start of the trial, the investigator is to decide based on clinical judgment whether it represents an AE as defined in the protocol, and if it is considered an AE then it must be reported accordingly. Please note,

that AEs, that get coded to terms like suicidal depression, suicidal ideation, suicidal threat or similar, are on the “Always serious AE List” and therefore must be reported as SAEs (refer to section [5.2.6.1.3](#)).

## **5.2.6 Assessment of adverse events**

### **5.2.6.1 Definitions of AEs**

#### **5.2.6.1.1 Adverse event**

An AE is defined as any untoward medical occurrence in a patient or clinical investigation subject administered a medicinal product and which does not necessarily have to have a causal relationship with this treatment.

An AE can therefore be any unfavorable and unintended sign (including an abnormal laboratory finding), symptom, or disease temporally associated with the use of a medicinal product, whether or not considered related to the medicinal product.

The following should also be recorded as an AE in the CRF and BI SAE form (if applicable):

- Worsening of the underlying disease or of other pre-existing conditions
- Changes in vital signs, ECG, physical examination and laboratory test results, if they are judged clinically relevant by the investigator.

If such abnormalities already exist prior to trial inclusion, they will be considered as baseline conditions and should be collected in the eCRF only.

Regarding AEs in the context of suicidal risk assessment by C-SSRS, section [5.2.5.1](#) should be adhered.

#### **5.2.6.1.2 Serious adverse event**

A serious adverse event (SAE) is defined as any AE, which fulfils at least one of the following criteria:

- results in death,
- is life-threatening, which refers to an event in which the patient was at risk of death at the time of the event; it does not refer to an event that hypothetically might have caused death if more severe,
- requires inpatient hospitalization or prolongation of existing hospitalization
- results in persistent or significant disability or incapacity,
- is a congenital anomaly / birth defect,
- is deemed serious for any other reason if it is an important medical event when based on appropriate medical judgement which may jeopardize the patient and may require medical or surgical intervention to prevent one of the other outcomes listed in the above definitions. Examples of such events are intensive treatment in an emergency room or at home for allergic bronchospasm, blood dyscrasias or convulsions that do not result in hospitalization or development of dependency or abuse.

For Japan only: the following events will be handled as “deemed serious for any other reason”. AEs which possibly lead to disability will be reported as SAEs.

#### 5.2.6.1.3 AEs considered “Always Serious”

In accordance with the European Medicines Agency initiative on Important Medical Events, Boehringer Ingelheim has set up a list of AEs, which by their nature, can always be considered to be “serious” even though they may not have met the criteria of an SAE as defined above.

The latest list of “Always Serious AEs” can be found in the EDC system. A copy of the latest list of “Always Serious AEs” will be provided upon request. These events should always be reported as SAEs as described in section [5.2.6.2](#).

Cancers of new histology and exacerbations of existing cancer must be classified as a serious event regardless of the time since discontinuation of the drug and must be reported as described in section [5.2.6.2](#), subsections “AE Collection” and “**AE reporting to sponsor and timelines**”.

#### 5.2.6.1.4 Adverse events of special interest

The term adverse events of special interest (AESI) relates to any specific AE that has been identified at the project level as being of particular concern for prospective safety monitoring and safety assessment within this trial, e.g. the potential for AEs based on knowledge from other compounds in the same class. AESIs need to be reported to the sponsor’s Pharmacovigilance Department within the same timeframe that applies to SAEs, please see section [5.2.6.2.2](#).

The following are considered as AESIs:

##### Hepatic injury

A hepatic injury is defined by the following alterations of hepatic laboratory parameters:

- An elevation of AST (Aspartate aminotransferase) and/or ALT (Alanine aminotransferase)  $\geq 3$  fold upper level of normal (ULN) combined with an elevation of total bilirubin  $\geq 2$  fold ULN measured in the same blood draw sample, or
- Aminotransferase (ALT, and/or AST) elevations  $\geq 10$  fold ULN.

These lab findings constitute a hepatic injury alert and the patients showing these lab abnormalities need to be followed up according to the “DILI checklist” provided in the EDC system. In case of clinical symptoms of hepatic injury (icterus, unexplained encephalopathy, unexplained coagulopathy, right upper quadrant abdominal pain, etc.) without lab results (ALT, AST, total bilirubin) available, the investigator should make sure these parameters are analyzed, if necessary in an unscheduled blood test. Should the results meet the criteria of hepatic injury alert, the procedures described in the DILI checklist should be followed.

No other AESIs have been defined for this trial.

#### 5.2.6.1.5 Intensity (severity) of AEs

The intensity (severity) of the AE should be judged based on the following:

- Mild: Awareness of sign(s) or symptom(s) that is/are easily tolerated.  
Moderate: Sufficient discomfort to cause interference with usual activity.  
Severe: Incapacitating or causing inability to work or to perform usual activities.

#### 5.2.6.1.6 Causal relationship of AEs

Medical judgement should be used to determine whether there is a reasonable possibility of a causal relationship between the adverse event and the given study treatment, considering all relevant factors, including pattern of reaction, temporal relationship, de-challenge or re-challenge, confounding factors such as concomitant medication, concomitant diseases and relevant history.

Arguments that may suggest that there is a reasonable possibility of a causal relationship could be:

- The event is consistent with the known pharmacology of the drug.
- The event is known to be caused by or attributed to the drug class.
- A plausible time to onset of the event relative to the time of drug exposure.
- Evidence that the event is reproducible when the drug is re-introduced.
- No medically sound alternative etiologies that could explain the event (e.g. pre-existing or concomitant diseases, or co-medications).
- The event is typically drug-related and infrequent in the general population not exposed to drugs (e.g. Stevens-Johnson syndrome).
- An indication of dose-response (i.e. greater effect size if the dose is increased, smaller effect size if dose is reduced).

Arguments that may suggest that there is no reasonable possibility of a causal relationship could be:

- No plausible time to onset of the event relative to the time of drug exposure is evident (e.g. pre-treatment cases, diagnosis of cancer or chronic disease within days / weeks of drug administration; an allergic reaction weeks after discontinuation of the drug concerned).
- Continuation of the event despite the withdrawal of the medication, taking into account the pharmacological properties of the compound (e.g. after 5 half-lives). Of note, this criterion may not be applicable to events whose time course is prolonged despite removing the original trigger.
- Additional arguments amongst those stated before, like alternative explanation (e.g. situations where other drugs or underlying diseases appear to provide a more likely explanation for the observed event than the drug concerned).
- Disappearance of the event even though the trial drug treatment continues or remains unchanged.

## 5.2.6.2 Adverse event collection and reporting

### 5.2.6.2.1 AE Collection

The investigator shall maintain and keep detailed records of all AEs in the patient files.

For patients who complete the treatment period, the following must be collected and documented on the appropriate CRF(s) by the investigator:

- From signing the informed consent onwards until the individual patient's end of trial (the EoTrial visit):
  - all AEs (serious and non-serious) and all AESIs.
- After the individual patient's end of trial:
  - the investigator does not need to actively monitor the patient for new AEs but should only report any occurrence of cancer and trial treatment related SAEs and trial treatment related AESIs of which the investigator may become aware of by any means of communication, e.g. phone call. Those AEs should be reported on the BI SAE form (see section [5.2.6.2.2](#)), but not on the CRF.

For patients who discontinue treatment prematurely and continue follow-up in the study (see section [6.2.3](#)), the following must be collected and documented on the appropriate CRF(s) by the investigator:

- From signing the informed consent onwards until the 28 days after the last study drug administration:
  - all AEs (non-serious and serious) and all AESIs.
- After 28 days follow-up until the individual patient's end of trial:
  - cancers of new histology and exacerbations of existing cancer, all trial treatment related SAEs and all trial treatment related AESIs.
- After the individual patient's end of the trial:
  - the investigator does not need to actively monitor the patient for new AEs but should report any occurrence of cancer and trial treatment related SAEs and trial treatment related AESIs of which the investigator may become aware of by any means of communication, e.g. phone call. Those AEs should be reported on the BI SAE form (see section [5.2.6.2.2](#)), but not on the CRF.

Patients who discontinue trial medication prematurely, who agree to be contacted further but do not agree to physical visits, should be followed up as described in section [3.3.4.1](#), withdrawal from trial treatment. From then on until the individual patient's end of the trial the investigator must report all deaths/fatal AEs regardless of relationship, and trial treatment related SAEs and trial treatment related AESIs the investigator becomes aware of.

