##### 3.3.4.1 Discontinuation of trial treatment

An individual patient will discontinue trial treatment if:

- The patient wants to discontinue trial treatment, without the need to justify the decision.
- The patient has repeatedly shown to be non-compliant with trial procedures and, in the opinion of both, the investigator and sponsor representative, is not willing or able to adhere to the trial requirements in the future.
- The patient can no longer receive trial treatment for medical reasons (such as surgery, AE, or other diseases), per investigator's clinical judgement.

- The patient shows disease progression/worsening that precludes further participation in the trial per investigator's clinical judgement.
- The participant develops suicidal ideation of type 4 or 5 in the C-SSRS (i.e., active suicidal thought with intent but without specific plan, active suicidal thought with plan and intent) or suicidal behavior (i.e. actual attempt, interrupted attempt, aborted attempt or preparatory acts or behavior).
- Any Non-suicidal self-injury that impacts safety of the study participant and jeopardize continued participation in the trial as per the clinical judgement of investigator.
- Pregnancy occurs during the trial.

If new efficacy/safety information becomes available, Boehringer Ingelheim will review the benefit-risk-assessment and, if needed, pause or discontinue the trial treatment for all patients or take any other appropriate action to guarantee the safety of the trial patients.

Even if the trial treatment is discontinued, the patients should remain in the trial and, given their agreement, will undergo the procedures for early treatment discontinuation and follow-up as outlined in the [Flow Chart](#) and section [6.2.3](#).

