### **7.8.1 Adverse Events**

The analyses of adverse events will be descriptive in nature. All analyses of AEs will be based on the number of patients with AEs and not on the number of AEs. The reporting and analyses of AEs will follow the BI guideline (12). AEs will be coded with the most current version of MedDRA.

For analysis of AE attributes such as duration, severity, etc. multiple AE occurrence data on the CRF will be collapsed into one AE event if all the following apply:

- All AE attributes are identical (LLT, intensity, action taken, therapy required, seriousness, reason for seriousness, relationship, and outcome).
- The occurrences were time-overlapping or time-adjacent (time-adjacency of 2 occurrences is given if the second occurrence started on the same day or on the day after the end of the first occurrence).

For further details on summarisation of AE data, please refer to ([5](#), [12](#)).

The analysis of AEs will be based on the concept of treatment emergent adverse events, thus, all adverse events occurring between the date of the first administration of trial treatment through the date of the last administration of trial treatment + residual effect period will be assigned to the on-treatment period. Adverse events that occur before first drug intake will be assigned to 'screening', and adverse events that occur within 28 days after the residual effect period will be assigned to 'follow-up'. For details on the treatment definitions, see [Section 6.1](#).

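### Protocol 5.2.5.1 and 5.2.6.2.1 conflict on reporting suicidality more than 28 days after last dose in early discontinuers who keep attending, and the list for that group omits unrelated deaths

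*Protocol*

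**What the plan says.** Protocol 5.2.5.1 sets the suicidality rule: "All C-SSRS reports of suicidal ideation type 4 or 5 and all reports of suicidal behavior must be reported as separate SAEs". It attaches no condition on causality or on time since last dose. Protocol 5.2.6.1.1 points to that rule: "Regarding AEs in the context of suicidal risk assessment by C-SSRS, section" 5.2.5.1 is to be followed.

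Protocol 5.2.6.2.1 sets the collection rule for patients who stop drug early and continue in the study. It has two stages before end of trial:

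- "From signing the informed consent onwards until the 28 days after the last study drug administration": all AEs and all AESIs.
- From that point to the end of the patient's participation, a shorter list applies: "cancers of new histology and exacerbations of existing cancer, all trial treatment related SAEs and all trial treatment related AESIs".

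For early discontinuers who accept contact but not physical visits, the same section says "the investigator must report all deaths/fatal AEs regardless of relationship", together with related SAEs and related AESIs.

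Footnote 18 of the Flow Chart sends patients who discontinue early and keep attending to 5.2.6.2.1 for their AE reporting requirements. The Flow Chart schedules the C-SSRS at every visit. It does not attach footnote 7, which marks procedures dropped after early discontinuation, to that row.

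Protocol 3.3.4.1 includes among the reasons to stop treatment: "The participant develops suicidal ideation of type 4 or 5 in the C-SSRS", or suicidal behaviour.

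On the analysis side, SAP 7.8.1 says "adverse events that occur within 28 days after the residual effect period will be assigned to" follow-up, and plans a separate table of AEs in that period. SAP 6.1 sets the residual effect period for safety at 28 days.

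**The concern.** Take a patient who stopped drug early, still attends, and has a suicide attempt six weeks after the last dose that the investigator judges unrelated. Under 5.2.5.1 this is an SAE report. Under 5.2.6.2.1 it is not on the list for that period. Two sites could each follow the protocol and handle the event differently.

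The relationship judgement therefore carries much of the weight. Protocol 5.2.6.1.6 gives implausible timing, persistence after drug withdrawal and underlying disease as arguments against causality. All three are easy to apply to suicidality in borderline personality disorder more than a month off drug.

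The rule for deaths is also uneven within one section. Patients reached only by phone have an explicit line for all deaths; patients seen in clinic do not, and no reason is given.

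This matters because suicidality is a stated safety assessment (Protocol 2.2.3), and Protocol 1.1 cites a rate of completed suicide 50 times that of the general population. Suicidality is itself a reason to stop treatment, so the group under the shorter list includes patients at raised risk.

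**Working it through.** **The rules side by side**, for an early discontinuer who keeps attending, more than 28 days after last dose:

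| Event judged unrelated | Broad reading | Narrow reading |
|---|---|---|
| C-SSRS type 4/5 ideation or suicidal behaviour | SAE (5.2.5.1, reached through 5.2.6.1.1; 5.2.6.2.2 sets no causality limit) | Not listed (5.2.6.2.1, reached through Flow Chart footnote 18) |
| Death | SAE by definition (5.2.6.1.2; 5.2.6.2.2) | Not listed for attending patients; listed for phone-only patients (5.2.6.2.1) |
| Cancer | Always serious, regardless of time since drug (5.2.6.1.3) | Listed, any relationship (5.2.6.2.1) |

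Cancer is the model case: its exception from 5.2.6.1.3 was carried into 5.2.6.2.1. The suicidality rule, which is just as categorical, was not.

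**How long the period lasts.** Inputs: full collection to last dose + 28 days (5.2.6.2.1). End of trial for attending discontinuers is Week 12 (Day 85), or four weeks after end of treatment if later (6.2.3). Visit days are the planned days in the Flow Chart. With L the day of last dose:

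- first day of the restricted period = L + 29
- length in days = max(0, 85 − (L + 28)) = max(0, 57 − L)

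| Last dose | Restricted period | Days | Scheduled C-SSRS assessments |
|---|---|---|---|
| Day 1 | Days 30–85 | 57 − 1 = 56 | 8 |
| Day 8 | Days 37–85 | 57 − 8 = 49 | 7 |
| Day 15 | Days 44–85 | 57 − 15 = 42 | 6 |
| Day 29 | Days 58–85 | 57 − 29 = 28 | 4 |
| Day 43 | Days 72–85 | 57 − 43 = 14 | 2 |
| Day 56 | Day 85 | 57 − 56 = 1 | 1 |
| Day 57 or later | none | 0 | 0 |

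For a last dose on Day 8 the seven assessments fall on Days 43, 50, 57, 64, 71, 78 and 85. Those on Days 50, 64 and 78 are phone visits.

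**Who feeds the SAP follow-up table.** A completer takes the last dose the day before EoT, and the End of Trial visit is at EoT + 28. That is 1 + 28 = 29 days after last dose, or 27 to 31 days with the ±2-day window. Completers therefore contribute at most about 31 − 28 = 3 days beyond the 28-day residual effect period. The same holds for discontinuers who decline further study visits and complete only FUP1, FUP2 and End of Trial. Almost all follow-up time in that table comes from early discontinuers who stay on, the group with the restricted list.

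The plan states no figure for this point, so there is none to reproduce.

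**The case against.** The strongest reply is that the protocol already settles the matter. Section 5.2.6.1.1 sends C-SSRS events to 5.2.5.1, the more specific rule, and 5.2.6.2.2 requires SAEs to be reported within 24 hours with no causality condition. Section 5.2.6.2.1 concerns what is collected on the CRF, which is a different duty from reporting to the sponsor, and the bullet does not contain the word only. This shows that a site could properly report. It does not remove the conflict: footnote 18 names 5.2.6.2.1 as the place for these patients' AE reporting requirements, and a second, shorter list after a first list of all AEs has a purpose only if it narrows.

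A reader might infer that suicidality and deaths would go unrecorded. The documents do not support that. The C-SSRS continues and is captured on the rater tablet, those entries are source data (8.3.1), and 5.2.6.2.1 opens by requiring records of all AEs in the patient files. The stated endpoint is suicidality by C-SSRS, which does not depend on the AE pages. A death is an SAE by definition and can be read as reportable under 5.2.6.2.2. Nor is it exact to say that the late list holds only drug-related events, since cancers are listed whatever their relationship.

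Narrower AE collection late after dosing is also defensible in general. Protocol 7.2.2.1 equates 7 days with three half-lives, so 28 days is 28 ÷ 7 × 3 = 12. That supports shorter collection for ordinary AEs. It does not explain why one section requires a suicidality SAE and another leaves it off the list.

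Finally, a reader might take the dropout allowance, 355 − 285 = 70 patients, as the number affected. It is a sample-size allowance. It does not say who stops before Day 57 or who then keeps attending.

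**Conclusion.** The conflict is real and worth fixing, and its reach is limited. As written, the protocol gives two answers on whether C-SSRS type 4/5 ideation and suicidal behaviour more than 28 days after last dose are SAEs regardless of relationship in early discontinuers who keep attending. It also omits unrelated deaths from the list for that group while naming all deaths for phone-only patients.

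The supported consequence is that such events may be absent from the AE/SAE CRF data and be treated differently between sites. The SAP follow-up AE table would then be selectively filled wherever sites followed 5.2.6.2.1. It would not necessarily understate events, because sites following 5.2.5.1 and 5.2.6.2.2 would report them. AE tables for the on-treatment period are unaffected, since they end at last dose + 28 days and collection is complete for attending patients until then.

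Exposure runs from 1 to 56 days per patient, for last doses on Days 56 down to 1, on planned visit days. The number of patients is unknown.

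**What to change.** In Protocol 5.2.6.2.1, extend the bullet for the period after the 28-day follow-up, for attending early discontinuers. It should say that all deaths, all C-SSRS type 4/5 ideation and all suicidal behaviour are documented and reported regardless of relationship until the individual patient's end of trial. Cross-refer to 5.2.5.1 so that the two sections and footnote 18 agree.

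In the phone-only paragraph, add the same C-SSRS suicidality categories. Deaths are already covered there.

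In SAP 7.8.1, note that, apart from these categories and cancers, the follow-up AE table contains selectively collected events, mostly from early discontinuers.

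The cost is protocol wording, a CRF-completion note and one SAP sentence. No assessment is added, because the C-SSRS is already scheduled at these visits. The downside is a few more SAE reports.

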### 3. DESCRIPTION OF DESIGN AND TRIAL POPULATION

#### 3.1 OVERALL TRIAL DESIGN

This is a Phase II, 12-week multi-center, multi-national, randomized, double-blind, placebo-controlled parallel-group trial in patients with BoPD. A targeted total of 355 patients with BoPD meeting the entry criteria are planned to be randomized into this trial.

V = Visit, W = Week, FUP = Follow-up, EoT = End of treatment, EoTrial = End of trial  
 ☎ = Telephone visit

Figure 3.1: 1 Study design

Patients will be enrolled into the trial once consent has been signed. Patients suitable after screening will be randomized to the 12-week double-blind treatment period at Visit 2 and will be assigned to placebo or one of the four treatment groups in 2.5:1:1:1:2 ratio (Figure 3.1: 1).

After the completion of the 12-week double-blind treatment period or following early discontinuation of trial medication at any point, patients will complete the 4-week follow-up period. Individual patient participation is concluded when the patient has completed their last planned visit (End of Trial visit). Safety will be formally evaluated at each visit until the end of the observational period which is 28 days after the end of treatment or for a longer time in case of unresolved AEs.

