### 7.2.5 Safety analyses

Adverse events will be coded using the Medical Dictionary for Drug Regulatory Activities (MedDRA). Standard BI summary tables and listings will be produced. All adverse events with an onset between start of treatment and end of the period of 28 days after the last dose of trial medication, will be assigned to the on-treatment period for evaluation.

All treated patients will be included in the safety analysis. In general, safety analyses will be descriptive in nature and will be based on BI standards. No hypothesis testing is planned.

Statistical analysis and reporting of adverse events will concentrate on treatment-emergent adverse events, i.e. all adverse events occurring between start of treatment and end of the REP. Adverse events that start before first drug intake and deteriorate under treatment will also be considered as 'treatment-emergent'.

Frequency, severity, and causal relationship of adverse events will be tabulated by system organ class and preferred term after coding according to the current version of the MedDRA at database lock.

Laboratory data will be analyzed both quantitatively as well as qualitatively. The latter will be done via comparison of laboratory data to their reference ranges. Values outside the reference range as well as values defined as clinically relevant will be summarized. Treatment groups will be compared descriptively with regard to distribution parameters as well as with regard to frequency and percentage of patients with abnormal values or clinically relevant abnormal values.

Vital signs, physical examinations, or other safety-relevant data observed at screening, baseline, during the course of the trial and at the end-of-trial evaluation will be assessed with regard to possible changes compared to findings before start of treatment.

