## 6. GENERAL ANALYSIS DEFINITIONS

### 6.1 TREATMENT(S)

For details on the treatment regimen, assignment of treatment groups, and the selection of doses, refer to Section 4 of the CTP. Below in Table 6.1:1 are the descriptions of the short and long names of the treatments. Next, are the definitions of the study phases for the analysis periods (Table 6.1:2).

Table 6.1: 1 Treatment descriptions

| Long Name            | Short Name |
|----------------------|------------|
| Placebo              | Placebo    |
| BI 1358894 5 mg qd   | BI 5 mg    |
| BI 1358894 25 mg qd  | BI 25 mg   |
| BI 1358894 75 mg qd  | BI 75 mg   |
| BI 1358894 125 mg qd | BI 125 mg  |

Table 6.1: 2 Study analysis phases\*

| Study analysis phase                        | Description                    | Start Date (included)                               | End Date (included)                                |
|---|--------------------------------|---|--|
| Screening phase                             | Screening (prior to treatment) | Date of informed consent                            | Date of first treatment administration minus 1 day |
| Treatment phase and residual effects period | On-treatment period            | Date of first treatment administration              | Date of last treatment administration + REP        |
| Follow-up phase                             | Off-treatment period           | Date of last treatment administration + REP + 1 day | Date of last CTP visit                             |

\* The defined treatment periods are the same for all treatment groups.

REP is the residual effect period which is defined as 28 days after the last dose of trial treatment for safety, and 7 days after last dose for efficacy

Dates are defined individually per patient. If more than one date is associated with a specific visit, measurements associated with a specific date are assigned to a study analysis phase according to the rules specified in the table. An analysis phase will not extend beyond the start date of the following phase.

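### The protocol contradicts itself on AE collection for early stoppers who accept contact but refuse all physical visits, and its narrower rule does not cover their 28-day on-treatment AE period

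*Protocol*

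**What the plan says.** Protocol 5.2.6.2.1 sets three collection rules:

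- **Completers:** all AEs and AESIs up to the end-of-trial visit.
- **Early stoppers who continue follow-up:** all AEs and AESIs "From signing the informed consent onwards until the 28 days after the last study drug administration", then a shorter list.
- **Early stoppers who accept contact but not physical visits:** "the investigator must report all deaths/fatal AEs regardless of relationship, and trial treatment related SAEs and trial treatment related AESIs", limited to events that come to the investigator's knowledge. This rule has no 28-day exception. Its period is given as "From then on until the individual patient's end of the trial", so its starting point is not dated.

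The paragraph with the third rule also sends these patients to 3.3.4.1, which refers on to the Flow Chart and 6.2.3. Section 6.2.3 makes the Flow Chart's phone-visit procedures obligatory, and the Flow Chart marks collection of all AEs, SAEs and AESIs at every phone visit. Protocol 3.1 adds: "Safety will be formally evaluated at each visit until the end of the observational period which is 28 days after the end of treatment".

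The analysis uses one window for all treated patients. In Protocol 7.2.5, AEs with onset from the start of treatment to the "end of the period of 28 days after the last dose of trial medication, will be assigned to the on-treatment period for evaluation". SAP 6.1 agrees: "REP is the residual effect period which is defined as 28 days after the last dose of trial treatment for safety". SAP 7.8.1 sets the counting unit: "All analyses of AEs will be based on the number of patients with AEs and not on the number of AEs".

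**The concern.** An AE that is not collected enters the tables as no AE. If a phone-only patient is followed under the narrow list, part of the period analysed as on-treatment is not fully observed, yet the patient stays in the denominator. Nothing in the SAP shortens the window for such a patient or identifies them.

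Patients who stop early include those who stop for an AE, worsening, suicidality or self-injury (Protocol 3.3.4.1). Protocol 7.2.2.1 and SAP 7.4.1 both bring safety into the choice of target dose, so the AE tables matter beyond description. Because the dedicated AE section and the Flow Chart disagree, two sites acting in good faith could also collect different data on similar patients.

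**Working it through.** **1. The instructions for one phone-only patient, side by side**

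| Source | What is required in the 28 days after last dose |
|---|---|
| Protocol 5.2.6.2.1, last paragraph | Fatal AEs, related SAEs, related AESIs |
| Protocol 3.3.4.1, then 6.2.3 and Flow Chart phone visits | All AEs, SAEs and AESIs |
| Protocol 3.1 | Safety evaluated at each visit to 28 days |
| Protocol 7.2.5; SAP 6.1 and 7.8.1 | All AEs analysed as on-treatment |

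Only the first row is out of line. The Flow Chart footnote on AEs refers to 5.2.6.2.1 for early stoppers who continue study visits, so it does not settle the phone-only case.

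**2. What the narrow list omits**

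It omits new non-serious AEs and non-fatal SAEs judged unrelated. There are exceptions. Protocol 5.2.5.1 separately requires C-SSRS ideation of type 4 or 5 and suicidal behaviour to be reported as SAEs. Protocol 5.2.6.1.3 separately requires cancers to be reported, although the phone-only list does not name them.

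**3. Share of a patient's on-treatment window affected**

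Read the narrow rule as starting when drug stops, which gives the maximum. For a stop after t days, the share is 28/(t + 28):

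- t = 14: 28/42 = 67%
- t = 28: 28/56 = 50%
- t = 56: 28/84 = 33%

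Under the 28-day rule for other early stoppers, the share is 0.

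**4. The plan's own figure**

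Protocol 7.5 gives 285 evaluable patients and 20% dropout. 285/0.80 = 356.25, against about 355 stated. By arm, 95/0.80 = 118.75 (119 stated), 38/0.80 = 47.5 (47) and 76/0.80 = 95 (95), and 119 + 3 × 47 + 95 = 355. The figure is reproduced to rounding. Planned dropouts are 0.20 × 355 = 71.

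**5. Effect on the percentage of patients with an AE**

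Under-count = d × s × q, where:

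- d = 20% (Protocol 7.5);
- s = phone-only share of early stoppers, **assumed** 10-50%, so 7.1 to 35.5 of 71 patients;
- q = chance that the patient's first AE falls in those 28 days and is outside the narrow list, **assumed** 10-40%.

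| s | q | d × s × q | Patients of 355 |
|---|---|---|---|
| 10% | 10% | 0.2 points | 0.7 |
| 25% | 20% | 1.0 point | 3.6 |
| 50% | 40% | 4.0 points | 14.2 |

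Because the SAP counts patients, only a first AE, overall or for a given term, changes a table.

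**The case against.** The strongest reply is that the protocol does not switch off AE collection. The paragraph with the narrow list itself starts a chain of references that ends at phone visits with full AE collection. The section also opens with a duty to keep records of all AEs, and an early end-of-treatment visit with AE and C-SSRS assessment is due soon after stopping. This stands: under-counting arises only where a site puts the narrow sentence first. It does not remove the conflict, because that sentence is the specific one, in the section written for AE collection.

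The group is also small. A reader might infer that 6.2.3 offers phone-only follow-up to anyone who stops early. It does not. The alternative there still asks for a clinic visit at Visit 8 or 9, and patients who decline study visits must still complete the three safety follow-up visits, of which only FUP2 is planned by phone. Refusal of all follow-up counts as withdrawal of consent. The narrow rule fits only patients who refuse every physical visit but take calls.

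The losses are limited too. An AE that led to stopping began before the narrow rule and should already be recorded. Protocol 7.2.2.1 equates 7 days with three elimination half-lives, so 28 days is about 28/(7/3) = 12, and much of the window carries little drug exposure. That bears on how many missed events would be drug effects. It does not bear on whether collection matches the window that the plan itself chose.

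**Conclusion.** The point holds as a contradiction that permits under-collection, not as a plain stop in collection. For phone-only early stoppers, the narrow sentence in 5.2.6.2.1 does not fit the Flow Chart, 3.3.4.1, 6.2.3, 3.1 or the 28-day analysis window. Where it is followed, the number of patients with AEs is too low, and collection could vary by site.

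The size cannot be derived from the documents. The range of 0.2-4.0 points (about 1 to 14 of 355 patients) rests on a planning dropout rate and two assumed inputs. For a single affected patient, the gap is at most 28 days of the window.

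Three stronger readings are not supported:

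- **All such collection ends on the day of stopping.** The start of the narrow rule is undated.
- **All unrelated SAEs are lost.** Fatal events and the C-SSRS events above remain reportable.
- **A poorly tolerated dose will look safer.** The error can only be towards too few AEs, but nothing in the documents shows that refusal of visits depends on dose. Differential bias is possible, not shown.

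**What to change.** Reconcile 5.2.6.2.1 with 3.3.4.1, 6.2.3, the Flow Chart, 7.2.5 and SAP 6.1/7.8.1. In the last paragraph of 5.2.6.2.1, apply the rule already written for other early stoppers: all AEs, SAEs and AESIs until 28 days after last dose, collected at the scheduled phone contacts. Start the reduced list only after that date.

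If some patients were already handled under the narrow rule, keep the common 28-day on-treatment period in SAP 7.8.1 and report, by arm, how many had reduced AE collection within it. Ending their on-treatment period early would be worse: deaths and related SAEs reported within the 28 days would move out of the on-treatment tables, and patients would have different residual effect periods.

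The cost is one sentence in the protocol, a CRF instruction and one line in a table. No visit is added. The downside is slightly more AE data entry for a few patients.
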